13.5 PREVENTION OF STUDY DROP-OUTS

Subjects will be encouraged to come for treatment and for the evaluation sessions as described in this protocol. To minimize missed sessions, they will be compensated for their transportation and time spent in completing study assessments. It will be emphasized to subjects during screening that even if they have a relapse they should come to all scheduled appointments. They will be discouraged from using cocaine, but there will be no penalty for relapsing, or for missed sessions.

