16.2.2 Secondary Outcome Measures

Measured reductions in cocaine and other drug use

- **A.** The proportion of successful subjects. A successful subject is one who reduces the overall proportion of cocaine use days to 75% or less of his/her baseline rate.
- **B.** The proportion of successful subjects. A successful subject is one who reduces the overall proportion of cocaine use days to 50% or less of his/her baseline rate.
- **C.** The proportion of successful subjects. A successful subject is one who reduces use days to 75% of his/her baseline level according to subject self report without regard to BE levels.
- **D.** Weekly proportion of non-use days according to subject self report without regard to BE levels.

- **E.** Weekly proportion of non-use days of other drug use, by other drug according to both SUR and urine toxicology results.
- **F.** Weekly mean urine BE level.
- **G.** Proportion of cocaine non-use days during the 8 week treatment period (non-use days divided by non-missing study days)
- **H.** The maximum number of consecutive cocaine non-use days.

Reduction in the severity of cocaine dependence and craving

- I. CGI-O scores.
- J. CGI-S scores.
- **K.** ASI scores.
- L. BSCS scores.

Severity of depression

M. HAM-D scores.

Safety of STS

AEs, laboratory data, physical exams, and vital signs.

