16.4 ANALYSIS PLAN

Each of the primary and secondary efficacy outcome measures will be analyzed for the intent-totreat and for the evaluable population. Major differences in the results, if any, will be further explored. While there is every intent to be complete in describing the analyses to be performed, it is not possible to anticipate every contingency and some adjustments may be required to meet constraints posed by the structure of the data.

All statistical tests will be two-sided at a 5% level of alpha. Confidence intervals will be two-sided with a 95% confidence coefficient.

Primary Efficacy Outcome

The primary outcome variable for each subject is the weekly proportion of cocaine non-use days. Each subject's weekly proportion is equal to the number of his/her cocaine non-use days divided by the number of his/her non-missing study days during that week (a maximum of 6 days for week 1 and 7 days for weeks 2 through 8).

The weekly mean proportion of cocaine non-use days on study will be compared between treatment groups using Generalized Estimating Equations (GEE). GEE provide a model-based regression methodology applicable for the analysis of the correlated data that will result from this repeated measures longitudinal study.

The GEE procedure proposed by Liang and Zeger¹⁸ and Zeger and Liang¹⁹ (Biometrics, 1986) model the population average and has several useful features:

- 1. It can be used to analyze different types of outcomes such as continuous, binary, or count.
- 2. It can be used to analyze an unbalanced design caused by either differing numbers of observations per person or by observations taken at different times.
- *3.* The parameter estimates are consistent even if assumptions about the variance structure are not completely accurate.

Secondary Efficacy Outcomes

As a secondary analysis, the baseline proportion of cocaine non-use days, site, gender, diagnosis of ADD, severity of depression during screening, and their first-order interactions with treatment will also be included in the model. Presentation will include the full model with all terms and a reduced model containing only significant terms.

Unless the primary response analysis implies the need for a more elaborate model, between group comparisons of the secondary outcomes will be performed as follows:

- 1. Proportion of successful subjects, measures A, B, and C, will be assessed by Chi-square tests.

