16.6 SAMPLE SIZE ESTIMATE

The proposed primary outcome measure is the weekly proportion of cocaine non-use days. Power analyses were made based on assumptions of normal distribution, equal correlation between observations at any two times (exchangeable) working correlation and a common standard deviation of 33.5%. These assumptions are based on preliminary results of an eightweek selegiline study (Protocol Number: CS-1017), in which an oral dose of selegiline was compared to placebo in cocaine dependent subjects. We further make the assumption that a 10% increase in the proportion of cocaine non-use days of the STS treatment group over the placebo group would be considered clinically significant. Based on the sample size calculation for GEE procedures proposed by Liu and Liang²⁰, then 110 subjects will be required in each arm to detect this clinically meaningful difference with a power of 80% at the 0.05 level of significance. The retention rates in studies of cocaine addicts currently being conducted by NIDA are approximately 70%, therefore at least 150 subjects should be randomized into each treatment to ensure an adequate sample size at the end of the trial.

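### Efficacy is scored on observed days only: the treatment difference can be biased if dropout acts differently in the two arms, and early leavers can count as successes on measures A–C

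*Protocol*

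**What the plan says.** **Primary analysis (Section 16.4).** The subject's weekly value is the count of non-use days "divided by the number of his/her non-missing study days during that week", with at most 6 days in week 1 and 7 thereafter. The arms are compared by Liang–Zeger GEE. One stated reason is that "It can be used to analyze an unbalanced design caused by either differing numbers of observations per person"; another is that estimates stay consistent if the variance structure is misjudged. The section names no weighting, missing-data assumption or working correlation. An exchangeable correlation appears only in the sample-size section (16.6).

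**Expected loss (Section 16.6).** "The retention rates in studies of cocaine addicts currently being conducted by NIDA are approximately 70" per cent.

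**Attendance (Section 13.5).** Subjects are told that "even if they have a relapse they should come to all scheduled appointments".

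**Missing-day rules (Section 16.2.1).** Reported non-use becomes missing if no urine test follows within 7 days, or if the subject's concordance is below 70%. Reported use is always kept.

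**Responders (Section 16.2.2).** Measure B reads: "A successful subject is one who reduces the overall proportion of cocaine use days to 50% or less of his/her baseline rate". Measure A is the same at 75%. C is a 75% rule on self-reported use days. None sets a minimum number of days. Measure G, the overall proportion, divides by non-missing days. Under Sections 16.3 and 16.4 all of these are analyzed in everyone randomized and again in the evaluable set.

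**The concern.** GEE accepts clusters of unequal size, but that does not make its estimate valid whatever the reason for the inequality. Unweighted GEE is generally consistent only when data are missing completely at random. When dropout depends on earlier observed outcomes, the result also depends on the working correlation, so the robustness that Section 16.4 claims no longer holds. Section 16.4 leaves that correlation open.

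The two arms could lose subjects differently. Section 4.4 lists application-site reaction, contact dermatitis, tachycardia and orthostatic hypotension as reasons for stopping the patch, and benefit could itself change retention. The arms would then be compared on differently selected weeks, and the intent-to-treat label would not prevent it.

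For the responder measures the problem is simpler. A proportion over a few days is noisy, so a short stay makes it easier to fall below a fixed fraction of baseline by chance.

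**Working it through.** **Inputs.** From Section 16.6: SD 33.5 points, target difference 10 points, exchangeable correlation, 150 per arm, about 30% loss. From Section 16.4: two-sided 5% level, eight weekly values. Scored days: 6 + 7 × 7 = 55.

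**1. The plan's own figure.** The correlation ρ is not stated. For an exchangeable GEE with 8 weeks,

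n per arm = 2 × [(1.960 + 0.842) × 33.5 / 10]² × (1 + 7ρ)/8 = 176.2 × (1 + 7ρ)/8.

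ρ = 0.5 gives 100, ρ = 0.57 gives 110 and ρ = 0.6 gives 115. The plan's 110 is reproduced at ρ of about 0.57, which is used below as an assumption.

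**2. Bias in the primary difference.** Weekly non-use percentages were simulated as normal with mean 50, SD 33.5 and ρ = 0.57. Dropout was permanent from week 2 on, with weekly hazard h × exp[–s × (y – 50)/33.5]. Here y is either the last observed week or the current, unseen week, s is 0, 0.7 or 1.2, and h was tuned to the stated loss. The GEE had week effects plus treatment and robust standard errors. Bias comes from 100,000 subjects per arm and rejection rates from 2,000 trials of 150 per arm. The Monte Carlo error of the bias is about 33.5 × √0.624 × √(2/100,000) = 0.12 points, slightly more with dropout.

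| Loss, placebo / STS | Dropout depends on | True effect | Bias, exchangeable | Bias, independence | Rejection, exch. / indep. |
|---|---|---|---|---|---|
| 30 / 30% | nothing | 0 | 0.12 | 0.12 | 4.7 / 4.7% |
| 30 / 30% | unseen week, both arms (s = 0.7) | 0 | 0.05 | 0.05 | 4.4 / 4.7% |
| 30 / 30% | unseen week, both arms (0.7) | 10 | 0.22 | 0.22 | 90.6 / 89.6% |
| 35 / 25% | unseen week, both arms (0.7) | 0 | –0.13 | –0.79 | 5.6 / 6.9% |
| 20 / 40% | unseen week, both arms (0.7) | 0 | 0.82 | 2.18 | 6.3 / 11.3% |
| 20 / 40% | last observed week, both arms (0.7) | 0 | 0.01 | 1.72 | 4.8 / 7.7% |
| 30 / 30% | last observed week, STS only (1.2) | 0 | 0.04 | 3.58 | 5.8 / 23.1% |
| 30 / 30% | unseen week, STS only (0.7) | 0 | 0.98 | 2.62 | 6.5 / 14.9% |
| 30 / 30% | unseen week, STS only (1.2) | 0 | 1.76 | 4.31 | 9.6 / 29.5% |
| 30 / 30% | unseen week, placebo only (0.7) | 10 | –1.24 | –2.94 | 83.2 / 65.1% |

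Positive bias favors STS. Three things follow:
- Use-related dropout that is the same in both arms barely moves the difference.
- Dropout that follows observed use is harmless with the correct exchangeable structure, but not with independence.
- Dropout tied to unseen use that differs between arms biases both, in either direction.

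**3. Early leavers on A and B.** Take 50% baseline use, no true change and independent days.
- 6 scored days, A: use ≤ 0.75 × 50% = 37.5%, so at most 2 use days; probability (1 + 6 + 15)/64 = 22/64 = 34%.
- 6 scored days, B: use ≤ 25%, so at most 1 use day; probability (1 + 6)/64 = 7/64 = 11%.
- 55 scored days: A needs at most 20 use days, probability 2.9%; B needs at most 13, probability under 0.1%.

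For baseline use of 40–70%, A is met with probability 18–34% at 6 days, against 0.2–6.3% at 55 days.

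One subject shows the mechanism. Two use days in 6 is 33%, which is 67% of a 50% baseline and a success on A. The same subject staying on at 50% use would reach (2 + 24.5)/55 = 48%, which is 96% of baseline and a failure.

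**4. Measure C.** If C is read as a count, 7 use days in the 14-day baseline sets the limit at 0.75 × 7 = 5.25. A six-day leaver then fails only by using on all six days, so succeeds with probability 1 – 1/64 = 98%.

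**The case against.** A reader might infer that the primary analysis is unbiased only if dropout is unrelated to use. That is too strong for the treatment difference: the same use-related dropout in both arms left it within 0.0–0.2 points of the truth.

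A reader might also infer that the protocol ties dropout to relapse. It does not. Section 13.5 urges attendance after a relapse, and Section 16.6 gives only a retention rate from other studies. The link is plausible but assumed. The rule in Section 16.2.1 that discards unconfirmed non-use while keeping reported use also cuts against the idea that missing days are mostly use days. What it does show is that missingness depends on the outcome by design.

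A quick product of gap and dropout difference, such as 30 points × 20% = 6 points, suggests a larger bias. It treats leavers as missing for all eight weeks, when they contribute the weeks before they leave. It also hides the direction: if more placebo subjects leave and then worsen, STS is understated.

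The protocol has real protections. Section 13.6 keeps subjects who stop the patch in scheduled assessments. Section 16.5 compares retention and missing counts between arms. Section 16.4 repeats each analysis in the evaluable set, whose requirement of 21 days of self report removes the six-day leaver. These soften the problem but do not repair the intent-to-treat result. Subjects who leave the study altogether are still lost, the comparison of counts is descriptive, and the evaluable set is selected on post-randomization data. Even at 21 scored days, the unchanged subject meets A with probability 9.5% and B with 1.3%.

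Finally, sensitivity analyses may sit in a SAP that is not shown, so their absence is not the point here. The point rests on what the protocol fixes: the denominators, the GEE rationale and the responder rules. A–C state no denominator of their own, so the early-leaver result holds if they are scored on observed days, as G is.

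**Conclusion.** The point stands in two parts.

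**Primary analysis.** The treatment difference can be biased if dropout differs between arms in rate or in its relation to use. The size is about 0–2 points with an exchangeable and up to about 4 points with an independence working correlation, against a planned effect of 10, in either direction. It is near zero if dropout acts alike in both arms. These figures rest on assumed dropout strengths, on ρ of about 0.57 and on normal weekly values. They show what is possible and do not forecast this trial.

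**Responder measures.** This part is the more concrete. With no follow-up requirement in the intent-to-treat set, an unchanged subject leaving after 6 scored days is about twelve times as likely to meet A as one followed for 55 days (34% against 2.9%), assuming independent days and scoring on observed days. The documents do not support reading this as proof of a false positive for STS: which arm gains depends on which arm loses more subjects early.

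The change should be made before unblinding.

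**What to change.** 1. **Section 16.4, primary comparison.** Fit it by a method valid under missing at random: either a likelihood-based repeated-measures model of the weekly proportions, or GEE weighted by the inverse probability of remaining on study. Name one, and fix the covariance or working correlation with it. Remove the suggestion that tolerance of unequal numbers of observations settles the missing-data question.
2. **Section 16.4, sensitivity analysis.** A missing-at-random method does not cover weeks of use that nobody saw. Fix one intent-to-treat analysis that scores every missing day as use, and read it beside the primary result. It is itself sensitive to unequal dropout, so it is a check and not a replacement.
3. **Section 16.2.2, measures A–C.** Count intent-to-treat subjects not followed to week 8 as non-successes, define what followed to week 8 means, and say whether C is a proportion or a count.

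The cost is protocol wording and some programming, with no extra data. The first change adds modelling assumptions. The third lowers absolute success rates and makes A–C reflect retention as well as reduced use, which their definitions should state.

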16.7 ADAPTIVE RANDOMIZATION PROCEDURE

Adaptive random allocation of subjects to study groups was developed to balance groups with respect to screening prognostic variables. The procedure allocates treatment assignment based on the assignments and prognostic variable levels for all previously enrolled subjects. The treatment groups will be balanced with respect to gender, diagnosis of ADD, historical self-report of cocaine use for the last 30 days at the time that informed consent is given (balanced for

 \geq 18 days of use and < 18 days of use), and severity of depression determined by HAM-D score (balanced for scores \geq 11 and <11). A new subject will be randomized with a "biased coin" procedure which uses randomization probabilities, favoring the treatment with the deficit enrollment, to improve the balance on group assignment (Efron¹⁰). The randomization process will be performed by computer at CSPCC.

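### The primary GEE is unadjusted although baseline use and the balancing factors are known before randomization: a valid test that gives up attainable power

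*Protocol*

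**What the plan says.** Section 16.4 defines the primary outcome as each subject's weekly proportion of cocaine non-use days and compares the treatment groups by GEE. No covariate is named. Under the secondary efficacy outcomes it continues: "As a secondary analysis, the baseline proportion of cocaine non-use days, site, gender, diagnosis of ADD, severity of depression during screening", together with the first-order interaction of each with treatment. Both the full model and "a reduced model containing only significant terms" are to be presented.

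Section 16.7 describes the allocation: "The treatment groups will be balanced with respect to gender, diagnosis of ADD, historical self-report of cocaine use for the last 30 days" (cut at 18 days), and HAM-D score. Sections 10.3 and 16.7 both call these screening prognostic variables.

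Sections 9.1, 10 and 14.1.2 require a 14-day baseline before randomization, with six urine specimens and daily self-report of use. This is the same kind of measure as the outcome.

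Section 16.6 sizes the trial without mentioning any covariate.

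**The concern.** The protocol itself gives adjustment secondary status, so this is a fixed choice and not a detail left to an analysis plan. It sits badly with the rest of the design. Allocation is steered to balance four variables because they are thought prognostic, and every subject completes a two-week baseline of the outcome measure, yet the primary test uses none of this.

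Nor is a plain adjusted estimate planned anywhere. The only adjusted model carries every treatment interaction, including those with about 16 sites (section 7). Its shortened form is chosen by looking at significance in the same data, so the p-values printed from it ignore that selection.

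At stake is power for the primary comparison, and the lack of a pre-specified main-effects result to set beside it.

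**Working it through.** **1. Which variables are used where**

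| Variable | Balanced in allocation | Primary GEE | Secondary model |
|---|---|---|---|
| Gender | yes | no | yes, and × treatment |
| ADD | yes | no | yes, and × treatment |
| HAM-D / depression severity | yes | no | yes, and × treatment |
| 30-day historical use | yes | no | **no** |
| 14-day baseline non-use | no | no | yes, and × treatment |
| Site | no | no | yes, and × treatment |

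**2. The plan's own sample size**

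Inputs, from sections 16.4 and 16.6:
- Level: "All statistical tests will be two-sided at a 5% level of alpha".
- Effect: "10% increase in the proportion of cocaine non-use days of the STS treatment group over the placebo group".
- Variability: "exchangeable) working correlation and a common standard deviation of 33.5" (per cent).
- Eight weekly values per subject ("a maximum of 6 days for week 1 and 7 days for weeks 2 through 8").
- Result: "110 subjects will be required in each arm to detect this clinically meaningful difference with a power of 80% at the 0.05 level".

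For a treatment-only GEE with exchangeable correlation ρ over 8 weeks:

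n per arm = 2 × [(1.960 + 0.842) × 33.5 / 10]² × (1 + 7ρ)/8 = 176.2 × (1 + 7ρ)/8

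The protocol does not give ρ. The formula yields 100 at ρ = 0.5, 110 at 0.57 and 115 at 0.6. So 110 is consistent with the inputs but cannot be fully reproduced. At ρ = 0.57 the SD of a subject's eight-week mean is 33.5 × √0.624 = 26.5 points.

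**3. Adding one baseline covariate**

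Let r be the correlation between baseline and on-study mean. It is **not in the documents**, so a range is shown. Residual variance falls by r², and at 110 per arm (level 0.05, ignoring the interim look):

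Power = Φ(2.802/√(1 − r²) − 1.960)

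| r | Variance removed | Power at 110 per arm | n per arm for 80% |
|---|---|---|---|
| 0 | 0% | 80.0% | 110 |
| 0.2 | 4% | 81.6% | 106 |
| 0.3 | 9% | 83.6% | 101 |
| 0.5 | 25% | 89.9% | 83 |
| 0.6 | 36% | 93.8% | 71 |

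**4. Several covariates, under biased-coin allocation**

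The formula prices one covariate only. A simulation used 220 subjects, biased-coin allocation on four binary factors with assumed prevalences, regression on subject means, and 1,500 runs per scenario. The adjusted model had baseline, gender, ADD and HAM-D as main effects, without site.

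| r | Type I error, unadjusted | Type I error, adjusted | Power, unadjusted | Power, adjusted |
|---|---|---|---|---|
| 0.3 | 4.7% | 5.2% | 79% | 81% |
| 0.5 | 4.2% | 5.3% | 81% | 91% |
| 0.6 | 4.2% | 4.8% | 79% | 93% |

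Monte Carlo error is about √(0.8 × 0.2/1500) = 1.0 point for power and √(0.05 × 0.95/1500) = 0.6 point for type I error. The conservatism of the unadjusted test is therefore slight.

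**5. Adding site**

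A further simulation at 220 subjects (4,000 runs, simple 1:1 allocation) used baseline, three binary factors and 16 sites as main effects, with site and factors assumed not prognostic. Power was 77.5% at r = 0.2, 79.4% at 0.3, 87.3% at 0.5 and 91.3% at 0.6. Against 80% unadjusted, the 15 site terms use up the gain when r is about 0.3 or less.

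**The case against.** The strongest reply is that nothing here is an error. An unadjusted comparison of randomized groups is valid and simple, and it matches the sample size, which assumes no adjustment. This stands: the loss is against the power the trial could have, not against the 80% it states.

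The second reply is that the gain rests on an unknown r. This also stands. Entry requires at least three positive specimens out of six (section 9.1), which narrows the baseline range and may lower r. At r = 0.2 to 0.3 the gain is only 2 to 4 points even under the one-covariate formula.

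Three stronger readings are tempting and are not supported:

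- *A reader might infer that balanced allocation makes the unadjusted test misleading.* The procedure is a probabilistic biased coin, how prognostic the factors are is not stated, and the simulated type I error of 4.2–4.7% is close to nominal and on the safe side.
- *A reader might infer that the treatment coefficient in the full interaction model is unusable.* That depends on coding, which section 16.4 does not state. With reference-cell coding the simulated standard error was about 13 to 15 points (about 3.5 unadjusted) and power was 10–12%. With mean-centred covariates, in a simulation with 300 subjects and r = 0.3, the standard error was 3.02, the same as for main effects only, with power 90.5% against 90.3%.
- *A reader might infer that adjustment is needed to make good a shortfall at 150 × 0.7 = 105 completers.* That is a separate matter. The intent-to-treat population is everyone randomized (section 16.3), and GEE accepts differing numbers of observations per subject, so 105 is not the analysis sample size.

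The criticism of the model cut to significant terms survives, but it concerns a labelled secondary presentation and not the primary inference.

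**Conclusion.** The point holds as a worthwhile and nearly free gain in efficiency, not as a fault in validity or in the stated power. Two parts can be read directly from the text and need no assumption. The primary model omits the baseline and all four balancing factors, with 30-day use absent from both models. And the only adjusted analyses planned are a full interaction model and one selected by significance.

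The size is conditional. It runs from about 2 points of power at r = 0.2 to 10 or more at r of 0.5 and above, for one covariate at 110 per arm with ρ back-solved to fit the stated sample size. Confidence is high on what the protocol omits and moderate at best on how much is gained.

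**What to change.** Before the interim analysis of section 16.8 and before any unblinding, amend section 16.4 as follows:

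- **Primary GEE:** treatment, week, baseline proportion of non-use days, gender, ADD, 30-day use (<18 / ≥18 days) and HAM-D category, as main effects only. The 14-day baseline and 30-day use overlap, but keeping both costs one parameter and respects the allocation.
- **HAM-D category:** first reconcile the cut. Section 10.3 splits at ≤11 / >11 and section 16.7 at ≥11 / <11, so a score of exactly 11 changes group. The model should use the split the randomization system applies.
- **Unadjusted GEE:** report as a sensitivity analysis.
- **Site:** leave out of the primary model or put it in a sensitivity analysis. It is not a balancing factor, and its roughly 15 terms could cancel the gain if r is about 0.3 or less and site is not prognostic.
- **Treatment interactions:** examine separately and label as exploratory.
- **Model reduced to significant terms:** drop it.

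The cost is wording only. Every covariate is collected before randomization, and the baseline rate is needed anyway because responder measures A to C in section 16.2.2 are defined against it. No visit, specimen or subject is added.
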